### **14.3. PROCEDURE AND CECUM REACHED TIME**

Time to cecum is defined as the net duration from insertion of the colonoscope to visualization of the cecum.

Time of the whole procedure is defined as the net duration from insertion of the colonoscope until removing of the whole instrument (guide: >6min withdrawal time).

Start & end time of any diagnostic or therapeutic intervention which will be performed during the insertion or retrograde phase, will be calculated and reduced from the total time.

### **14.4. CECAL INTUBATION**

Completion of colonoscopy with the MCS is defined from insertion of colonoscope to visualization of the cecum, confirmed by a snapshot.

Cecal intubation will be evaluated by the number of colonoscopy procedures that reached the cecum.

### **14.5. USER SATISFACTION**

User satisfaction will be evaluated by a questionnaire (specified in the CRF). The physicians who will conduct the procedures and the nurse who assists the procedure and assembles the MCS will be asked to fill-in a dedicated questionnaire in the CRF and include their feedback on the system.

---

 ASGE, Complications of colonoscopy, Gastrointestinal Endoscopy, Volume 74, No. 4 : 2011

 Dominitz J. A., et al., "Complications of Colonoscopy", Gastrointestinal Endosc.2003: 57(4): 441-445

## 15. STATISTICAL CONSIDERATIONS

### 15.1. DETERMINATION OF SAMPLE SIZE

The primary objective of the study is to evaluate the effectiveness of MCS in cleansing a poorly prepared colon.

Based on previous study data (pre-clinical and clinical), 36% and 96% success rates of good/excellent cleansing levels are have been found for pre procedure and post procedure, respectively.

A sample size of 47 patients is required as per McNemar test to determine that the paired discordant proportion are significantly different under the followings assumptions:

Probability of Type I Error ( $\alpha$ ) = 0.05

Power ( $1 - \beta$ ) = 0.8

Proportion switching from + to - = 0

Proportion switching from - to + = 0.6

Sample size required (number of pairs) = 11

This pilot study will include 3 sites (i.e., 2 sites in NL and 1 site in Germany). As per McNemar sample size calculation 11 subjects will be recruited per site.

Adding 10% of drop out (i.e. 4 cases) and additional 9 cases (The first 3 subjects of each physician) that will be excluded from the secondary analysis in order to compensate the system operation learning curve.

The overall sample size is as follows:

3 subjects per site for training - overall 9 subjects

11 subjects per site - overall 33 subjects

Addition of 10% of withdrawn subjects - 4 subjects

Therefore , up to 47 subjects (15-16 subjects per site) are planned to be enrolled to this study.

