## 1. PROTOCOL SYNOPSIS

Document ID:	CL00016
Title:	Evaluation of the performance of the Motus Cleansing System (MCS)
Study Sponsor	Motus GI Medical Technologies, [name] [contact] [contact] Israel
Sponsor Representative	[name], VP RA, Clinical and QA
European Authorized Representative (EAR)	OBELIS S.A , [name] Téléfono: [contact] , [contact] E-mail:[contact], www.obelis.net
Investigational Device:	Motus Cleansing System (MCS)
Indication for use	The MCS is intended to facilitate intra-procedural cleaning of a poorly prepared colon by irrigating the colon and evacuating the irrigation fluid and feces
Regulatory status	The MCS is a non CE marked, class IIa medical device.
Study Period	Study period will last approx. 6 months
Duration of Participation	The duration of subject participation in the study is expected to be a maximum of 16-19 days (i.e. 1-3 preparation days + colonoscopy procedure day + 14 days post procedure)
Study Design	Prospective, multi-center, single-arm, open-label study
Randomization	No randomization will be applied.
Sample Size	sample size of 47 patients is required to achieve improvement of 60 % in the rate of adequate cleansing rate between the pre and post procedure for the primary hypothesis.
Number of Subjects	Up to 47 eligible subjects ( 15-16 subjects per site)
Study Population	Subjects allocated for a screening, diagnostic or surveillance colonoscopy
Objectives	The main objective of the study is to demonstrate the performance of the Motus GI system used in conjunction with screening, diagnostic or surveillance colonoscopy
Study Endpoints and Measures	Primary Endpoint Pre and Post procedure adequate cleansing rate per subject Secondary Endpoint: Type, incidence, severity, and duration of adverse events

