## **11. SUBJECT POPULATION**

### **11.1. NUMBER OF SUBJECTS**

Up to 47 eligible subjects (up to 15-16 adult eligible subjects per site) that are candidates for diagnostic, screening or surveillance colonoscopy procedure will be enrolled in the study.

Subjects will be considered for the study if they meet the specific inclusion/exclusion criteria.

The criteria for enrollment must be strictly followed.

At least 15% from the entire population will be included in each of the sub groups (i.e., Screening, Surveillance, diagnostic)

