### **15.4. POOLING**

In addition to generating clinical reports from this study, data from the sites in this multi-center study and possibly from additional studies performed in other clinical centers following the same study design and using a common protocol may be pooled. In such a case the study data may be pooled and subgroup analysis of the primary endpoint by center will be used to evaluate the poolability of the results. The safety and clean rate by center interaction will be tested with appropriate standard statistical methods. Data from the user satisfaction questionnaires may be pooled later as well to be used in a future usability study.

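### Section 15.1 and the synopsis call 47 patients required, but the stated McNemar inputs give 11 pairs for the whole study; 15.1 also removes the lead-in subjects from the wrong analysis

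*Combined protocol and SAP*

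**What the plan says.** Section 15.1 states that "A sample size of 47 patients is required as per McNemar test". It then lists alpha 0.05, power 0.8, no subjects moving from adequate to inadequate and a proportion of 0.6 moving the other way. The result it prints is "Sample size required (number of pairs) = 11". It goes on: "As per McNemar sample size calculation 11 subjects will be recruited per site". To 33 subjects (11 at each of three sites) it adds 9 lead-in subjects and 4 for 10% dropout, and concludes that "up to 47 subjects (15-16 subjects per site) are planned to be enrolled to this study".

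The synopsis says that a "sample size of 47 patients is required to achieve improvement of 60" per cent in the adequate cleansing rate for the primary hypothesis. Its next row and section 11.1 give 47 as a maximum; 11.1 reads "Up to 47 eligible subjects (up to 15-16 adult eligible subjects per site").

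On the lead-in subjects, 15.1 excludes the first three of each physician from the secondary analysis. Section 14 excludes them from the performance evaluation and keeps them in the safety evaluation. Section 15.2.3 identifies the secondary endpoint as adverse events and puts every enrolled subject in the safety set. The efficacy exclusions in 15.2.1 do not mention lead-in subjects.

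For the primary comparison of pre- and post-procedure rates, 15.2.2 plans a chi-square or Fisher's exact test.

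**The concern.** Section 15.1 gives two different numbers as the McNemar requirement, and only one can be right. If 47 were a statistical requirement, enrolling fewer would leave the study short of its stated power. If it is a cap, the justification given for it in 15.1 and the synopsis is wrong. The step from 11 to 33 is credited to a calculation that contains no site term.

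The lead-in wording bears on who is analysed. Read literally, 15.1 takes 9 subjects out of safety and leaves them in the primary analysis, the reverse of section 14. No part of the statistical section states the rule of section 14.

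The test named in 15.2.2 treats two measurements on the same subject as independent samples, so it matches neither the design nor the sizing.

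**Working it through.** **Inputs (15.1).** Alpha = 0.05; power = 0.8, so z = 0.8416; p01 = 0.6; p10 = 0. Discordant total p01 + p10 = 0.6; difference d = p01 − p10 = 0.6, which agrees with the quoted rates of 36% before and 96% after. Sidedness is not stated; both cases are shown.

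**Reproducing the plan's 11.** Normal approximation for McNemar's test:

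n = [z_a·√(p01 + p10) + z_b·√(p01 + p10 − d²)]² / d²

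- Two-sided, z_a = 1.960: (1.960·√0.6 + 0.8416·√0.24)² / 0.36 = (1.518 + 0.412)² / 0.36 = 10.35, so **11 pairs**. This matches the plan.
- One-sided, z_a = 1.645: 7.90, so 8 pairs.

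The result is a total for one hypothesis. Nothing in the formula refers to sites.

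**Exact McNemar.** With p10 = 0, all b discordant pairs favour the device.

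- Two-sided p = 2 × 0.5^b. b = 5 gives 0.0625 and b = 6 gives 0.031, so b ≥ 6 is needed. P(Bin(11, 0.6) ≥ 6) = 0.753; P(Bin(12, 0.6) ≥ 6) = 0.842. Required: 12 pairs.
- One-sided p = 0.5^b, so b ≥ 5 is needed. P(Bin(9, 0.6) ≥ 5) = 0.733; P(Bin(10, 0.6) ≥ 5) = 0.834. Required: 10 pairs.

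**Could 47 be a McNemar result?** With p10 = 0, the two-sided formula gives 46.6 pairs at p01 = 0.16, so 47 pairs would correspond to p01 of about 0.16. The plan assumes 0.6.

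**Power at the planned size.** Approximate two-sided power = Φ[(0.6·√N − 1.960·√0.6) / √0.24].

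| Pairs | Normal approximation | Exact two-sided |
|---|---|---|
| 11 | 83.2% | 75.3% |
| 12 | – | 84.2% |
| 33 | above 99.9% | above 99.9% |

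**Build-up of 47.** 9 + 33 + 4 = 46. The base of the 10% is not given:

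- on 33: 3.3, which is 4 if rounded up, total 46;
- on 42 (33 + 9): 4.2, which is 4 if rounded to the nearest whole number, total 46;
- 42 × 1.1 = 46.2 and 42 / 0.9 = 46.7, both 47 if rounded up, which means 5 for dropout.

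**Lead-in subjects, side by side.**

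| Section | Performance (primary) | Safety (secondary) |
|---|---|---|
| 15.1 | not mentioned | excluded |
| 14 | excluded | included |
| 15.2.1 | not listed among exclusions | – |
| 15.2.3 | – | all enrolled |

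The count of 9 assumes one physician per site: 15.1 defines the lead-in by physician in one sentence and by site in its total.

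**Test named in 15.2.2.** Cell probabilities consistent with 15.1 are 0.36 (adequate both times), 0.60 (improved) and 0.04 (inadequate both times). Applying Fisher's two-sided test to 33 subjects as if the pre and post groups were independent gives power above 99.9%. The mismatch therefore costs no meaningful power here; it is a question of the correct test.

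**The case against.** The strongest defence is that 15.1 hides nothing. It prints 11 pairs, shows each addition and ends with a maximum, as do section 11.1 and a synopsis row. The fault then lies in a loosely worded lead sentence.

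The 11 per site could also be a deliberate choice to let each site stand alone. Section 15.4 makes pooling conditional and says that "subgroup analysis of the primary endpoint by center will be used to evaluate the poolability of the results". On that reading 33 is a conservative choice whose reason was left out.

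On the lead-in subjects, section 14 is explicit and 15.2.3 agrees with it, so one stray word in 15.1 is unlikely to change the analysis. The choice of test is arguably a separate matter, and the consequence for power is nil.

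Much of this is fair, and it limits the weight of the point: the build-up is open, and the study is larger than its stated test needs. It does not remove the error. No site-level hypothesis is written, the synopsis ties 47 to one primary hypothesis, and 15.1 gives the McNemar calculation itself as the source of 11 per site. Section 15.4 adds that "The safety and clean rate by center interaction will be tested with appropriate standard statistical methods", but nothing in the plan sizes the study for that test or for the by-centre analysis. The contradiction over the lead-in subjects remains in the text, and 15.2.1, where an analyst would look for the rule, omits it.

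**Conclusion.** The concern holds. The stated inputs require 11 pairs in total by the two-sided normal approximation, or 12 by exact two-sided McNemar; one-sided versions need 8 and 10. All are well below the 33 evaluable subjects planned and the 47 called required. This rests on p01 = 0.6 and p10 = 0 as stated, and on a two-sided test, which is assumed because it reproduces the plan's 11.

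The sizing error is towards more power and does not threaten the primary conclusion. The 46 against 47 gap is one subject under a cap and is minor. The contradiction over which analysis omits the lead-in subjects, and the unpaired test on paired data, matter more for the analysis and should be settled before it is run. The sponsor should correct all of these; none calls for a different enrolment.

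**What to change.** 1. In 15.1 and the synopsis, state that the McNemar calculation requires 11 pairs in total, naming the normal approximation and the intended sidedness; state 12 if the exact two-sided test is intended.
2. State that 33 evaluable subjects (11 per site) are planned, with power above 99% at p01 = 0.6, and that 47 is the enrolment cap. The sponsor should give its own reason for 11 per site.
3. State the base of the 10% dropout so that parts and total agree: 4 with 46, or 5 with 47.
4. In 15.1, name the performance (primary) analysis as the one that omits the lead-in subjects. List that exclusion in 15.2.1, using one unit throughout, physician or site.
5. In 15.2.2, name McNemar's paired test, in the same version (exact or asymptotic) as the sample-size statement.

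The cost is a text amendment. Items 4 and 5 touch the analysis plan, so they should be in place before the data are analysed. Enrolment and data collection stay as they are.

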### 15.2. DESCRIPTION OF STATISTICAL METHODS

Demographic and other baseline characteristics will be provided for all subject.

Summary statistics (arithmetic mean, standard deviation, median, minimum and maximum for quantitative variables) will be presented for the total study population. Frequency tables for qualitative data will be provided.

Any deviation from specified statistical plan will be in addition to “per protocol” analysis and will be reported as such. Post-hoc analysis will be conducted according to the existing data gathered, if necessary.

#### 15.2.1. ANALYSIS OF POPULATION

Subjects will be excluded from the efficacy analysis as missing/invalid data by the following:

- Subject withdraws
- Unprepared subjects (not taken the preparation or had a partial bowel preparation)
- System technical failure

Individual listings of withdrawal / failure including descriptive information will be provided.

In addition, in cases of incomplete procedure (i.e., the entire colon is not visualized); the overall BBPS per patient will be evaluated based on the colon segments that were visualized.

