#### **12.4. COLON PREPARATION PROTOCOL**

In a trial to mimic poorly prepped subjects, the subjects will be instructed to follow a limited preparation regimen. An example of proposed bowel preparation regimen is detailed below:

- Split dosing of Bisacodyl\* (2 tablets of 5mg in each dose):
  - First dose: 2 tablets Bisacodyl either in:
    - the early afternoon 1 day prior to colonoscopy (for morning procedures)
    - OR
    - the evening 1 day prior to colonoscopy (for afternoon procedures)
  - Second dose: 2 tablets Bisacodyl either in:
    - the evening 1 day prior to colonoscopy (for morning procedures)
    - OR
    - the early morning on the day of procedure (for afternoon procedures)

The following diet requirements will apply:

- From 2 days prior to colonoscopy until colonoscopy procedure: no dried fruits, seeds, nuts, legumes and a like.
  - Up to 24 hours prior to colonoscopy: clear liquid diet
  - Colonoscopy day: 3 hours before the procedure – no food/liquids
- \* Generic Bisacodyl will be used in the study as routinely used in the participating sites according to the indications of use but following the dosing regime shown above.

The bisacodyl should be use as detailed in the ICF and per the physicians instruction.

- Bisacodyl is taking whole ,by mouth with a full glass of water (8 oz/240 mL), with or without food.
- Drinking extra fluids while taking bisacodyl is recommended.
- Taking Bisacodyl within 1 hour after taking an antacid or milk is not allowed.

An example of the bowel preparation regimen for the subjects can be found in the Appendix C and in the ICF.

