## **12.5. COLONOSCOPY PROCEDURE (VISIT 2)**

### Pre-Examination Procedures

- Verify eligibility checked and informed consent was obtained after explaining all risks, benefits, and alternatives to the candidate.
- Verify that the research assistant has collected completed diaries from the subject.
- Verify all background/clinical information, demographic and medical history was documented
  - Note: Subjects that did not take the bowel preparation or failed to complete the bowel preparation will not undergo the procedure and will be excluded from the study.
- Verify all connections and assemblies are properly attached (see Instructions for Use “Setup and Interconnections” section and sections 5.4 and 5.5. in this protocol )
- Verify device works properly (see Instructions for Use “System Operation” section and sections 5.4 and 5.5. in this protocol)
- Place and prepare the subject for the procedure as per standard colonoscopy.
- Perform a digital rectal exam as per standard colonoscopy , evaluate the adequate level of the preparation and start the colonoscopy procedure as per standard of care.

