### **12.6. DIARIES:**

Subject diaries are provided to the subject at visit 1 to be filled by the subjects during the preparation phase. This will include diet and bowel movement information. The subject is instructed to bring the diary with him/her to the scheduled colonoscopy.

Additional questions regarding basic demographic information, and health assessment will be filled out in the CRF by the study team.

All subjective assessment questions recorded in the CRF may be used in future studies.

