### **15.5. HANDLING OF MISSING DATA**

Dropouts and subjects lost to follow will be treated as missing values and therefore dropped from analysis of performance variables. A subject for whom the procedure was not performed to due to no or partial bowel preparation will not be entered into this analysis. No imputation of missing data will be performed.

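### Section 15.2.1 allows a subject already treated and scored to be dropped from efficacy for partial preparation; section 15.5 does not

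*Combined protocol and SAP*

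**What the plan says.** Three sections of the combined protocol and SAP deal with subjects whose bowel preparation was absent or incomplete.

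- **Section 12.5, Pre-Examination Procedures:** "Subjects that did not take the bowel preparation or failed to complete the bowel preparation will not undergo the procedure", and they are excluded from the study.
- **Section 15.2.1:** "Subjects will be excluded from the efficacy analysis as missing/invalid data by the following", followed by a list of three reasons. One of them is "Unprepared subjects (not taken the preparation or had a partial bowel preparation"). The other two are withdrawal and technical failure of the system.
- **Section 15.5:** "A subject for whom the procedure was not performed to due to no or partial bowel preparation will not be entered into this analysis". The section adds: "No imputation of missing data will be performed".

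Three other parts of the plan bear on how these rules would work.

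- The study is open-label with no blinding (section 15.3), and BBPS is scored by the colonoscopist (section 14.1). Blinded central re-reading is only an option (Appendix A).
- Section 25 says that a subject treated in a way that deviates from the protocol, or admitted without qualifying, may be ineligible for analysis.
- Section 12.6 says of the preparation diary: "This will include diet and bowel movement information". Section 12.5 has staff confirm that diaries were collected. Neither section names a record of bisacodyl intake, and no section says which elements make preparation complete or partial.

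**The concern.** The two analysis rules do not cover the same people. Section 15.5 makes the exclusion depend on the procedure not having been done. Section 15.2.1 has no such condition. A subject who passed the pre-examination check, had the device used and was scored before and after cleansing is therefore in the efficacy set under one rule and can be out under the other. The plan does not say which rule governs.

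An exclusion decided before insertion cannot depend on the outcome. One decided afterwards can, because the scores are known and come from an unblinded operator. If a treated subject with a poor result is reclassified as partially prepared, the reported post-procedure rate rises. The baseline rate set against it changes as well. The primary objective is performance in a poorly prepared colon, so subjects whose preparation fell short are not obviously outside the target population.

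**Working it through.** **1. The rules side by side**

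| Situation | 15.5 | 15.2.1 |
|---|---|---|
| No or partial preparation, stopped at the 12.5 check, no procedure | excluded | excluded |
| Partial preparation found or judged after insertion, subject scored | kept | can be excluded |

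The rules differ only in the second row. That row is empty if the 12.5 check catches every case.

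**2. The plan's own sample size**

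Inputs from section 15.1: alpha 0.05 (taken as two-sided, since the plan does not say), power 0.80, proportion switching from adequate to inadequate 0, and from inadequate to adequate 0.6. The discordant proportion pd and the difference d are both 0.6.

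n = [1.960 × √0.6 + 0.842 × √(0.6 − 0.36)]² / 0.36 = (1.518 + 0.412)² / 0.36 = 10.35, rounded up to 11.

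This reproduces the stated 11 pairs. At 11 per site, three sites give the planned 33 evaluable subjects. The point disputes none of these figures.

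**3. Effect on the post-procedure rate**

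The documents give no adherence rate and no number of late reclassifications, so the counts here are assumed. Take 33 evaluable subjects with 3 post-procedure failures and drop k of those failures. The rate is 30/(33 − k).

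| k | Rate | Exact (Clopper-Pearson) 95% CI |
|---|---|---|
| 0 | 30/33 = 90.9% | 75.7 to 98.1 |
| 1 | 30/32 = 93.8% | 79.2 to 99.2 |
| 2 | 30/31 = 96.8% | 83.3 to 99.9 |
| 3 | 30/30 = 100% | 88.4 to 100 |

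A milder case has one failure, which is dropped: 32/33 = 97.0% (84.2 to 99.9) becomes 32/32 = 100% (89.1 to 100). At the planning post-procedure rate of 96%, the expected number of failures is 33 × 0.04 = 1.3, so the milder case is closer to the plan's own expectation.

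**4. Effect on the pre/post comparison**

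Assume 12/33 adequate at baseline (36.4%, close to the planning value of 36%), no subject moving from adequate to inadequate, and the same 3 failures inadequate both before and after.

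- All 33 kept: 30/33 − 12/33 = 18/33 = 54.5 percentage points.
- The 3 dropped: 30/30 − 12/30 = 18/30 = 60.0 percentage points.

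The post-procedure rate rises by 9.1 points and the baseline rate by 3.6 points (36.4% to 40.0%). The difference therefore rises by 5.5 points.

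**5. Effect on the primary test**

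The three dropped subjects are concordant pairs. There are 18 discordant pairs either way, all in one direction, so the exact two-sided McNemar p-value is 2 × 0.5¹⁸ = 0.0000076 in both cases. Section 15.2.2 names a chi-square or Fisher test instead. Fisher's test on 12/33 against 30/33, and on 12/30 against 30/30, gives p below 0.00001 both times.

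For power, the exact two-sided McNemar test needs at least 6 discordant pairs when all go one way (2 × 0.5⁶ = 0.031; 2 × 0.5⁵ = 0.063 is not enough). With a switching proportion of 0.6, the chance of at least 6 exceeds 0.99 at 29, 30 or 33 pairs. What is at risk is the reported rates and their intervals, not the test.

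**The case against.** The strongest reply is that section 12.5 already settles the matter. Incompletely prepared subjects do not have the procedure, so nobody is both partially prepared and scored. On that reading, 15.2.1 is a short list of reasons and 15.5 states the same reason in full. This stands as far as it goes: the gap opens only after a deviation or a late discovery. But an analysis rule is needed for exactly those cases, and here the two sections give different answers.

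A second reply is that the size is speculative. That is fair. The failure counts are assumed, nothing in the documents shows that late reclassification would follow a poor result, and the effect on the primary test is negligible.

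A third reply is that exclusions would not be silent. Section 13 requires withdrawal reasons to be recorded and all enrolled subjects to be accounted for, and 15.2.1 promises individual listings of withdrawals and failures. That helps a reader see an exclusion after the fact. It does not decide who belongs in the denominator.

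A reader might infer that the diary omits the bisacodyl doses, so that adherence is judged without dose data. The documents do not support this. The diary form and the CRF are not included, and the description in section 12.6 need not be exhaustive. Appendix C has time blanks beside each dose, although it is an instruction sheet and subjects are told to bring only their diaries. What can be said is that the protocol does not specify which record documents intake.

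A reader might also infer that partial could mean any diet lapse. Appendix C heads the tablet doses as bowel preparation and lists diet separately, which favours a narrower reading. Section 12.4 puts tablets and diet under one preparation protocol, so some ambiguity remains.

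**Conclusion.** The point holds in a limited form. Sections 15.2.1 and 15.5 conflict for one kind of subject: treated with the device, scored, and only then found or judged to have been partially prepared. For that subject, 15.2.1 permits an exclusion made with the outcome known and the operator unblinded, which can bias the reported rates.

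In the illustration, the post-procedure rate moves by up to 9.1 points and the pre/post difference by 5.5 points. With a single failure dropped, the post-procedure rate moves by 3.0 points (97.0% to 100%). These sizes rest on assumed counts and on every reclassified subject being a failure both before and after. The primary conclusion would not change.

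It would go too far to say that the plan intends outcome-dependent exclusion or that such exclusions are likely. The text leaves the route open, and closing it is nearly free.

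**What to change.** Reword 15.2.1 to match 15.5: no or partial preparation excludes a subject from efficacy only when the procedure was not performed for that reason. Add that a subject in whom the MCS was used is not removed from the efficacy set on preparation grounds, including under the deviation clause in section 25. State that the separately planned exclusions are unaffected: each physician's first 3 subjects (section 14), withdrawal, and system technical failure (15.2.1). The pre-procedure check in 12.5 is not touched.

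The cost is a sentence or two in the analysis section. The downside is that a few imperfectly prepared subjects stay in and may slightly lower the reported rate.

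As a secondary clarification only, 12.5, 12.6, 15.2.1 and 15.5 should be reconciled on which record documents bisacodyl intake and which elements make preparation complete. Which elements count is for the sponsor to decide.

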#### 3.2. PRE-CLINICAL & CLINICAL TESTING

Pre-clinical testing, including electrical and mechanical design testing, biocompatibility, reliability tests, software validation and animal studies were conducted in compliance with the applicable international standards and the essential requirement of the Medical Device Directive 93/42/EEC (MDD) to the MCS (Please refer to the Investigator’s Brochure section “Pre-clinical Testing” for more information). To date, clinical trials were performed using various versions of the MCS (including the current version) and demonstrated 95%-100% cleansing capabilities in poorly prepped subjects. The

---

 Adenoma Detection on Repeat Colonoscopy after Previous Inadequate Preparation, Colin L Smith, Journal of Gastroenterology and Hepatology research, Vol 2, No 12 (2013)

subjects were prepped with reduced preparation doses relatively to those that are standardly used, including the same preparation regime that is described in this protocol. Detailed information on the pre-clinical & clinical testing is provided in the Investigator's Brochure, section "Pre-Clinical & Clinical experience with the device".

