#### **4.4. RISK ASSOCIATED WITH THE PARTICIPATION IN THE CLINICAL INVESTIGATION**

The potential risks associated with the participation in the clinical investigation may include a repeated colonoscopy procedure as the subjects enrolled to the study are required to undergo a limited prep as compared to the preparation given prior to standard colonoscopy procedure to mimic a poor colon preparation.

Based on previous clinical data an excellent cleansing effectiveness was demonstrated following the use of the MCS device ; MCS improved the cleansing level from 30% at baseline to 93% after the cleansing was operated, where the preparation in these studies were identical to the preparation in current study, for further detailed please refer to the "clinical evaluation report" (see pages 5-8 of the Risk Benefit assessment document).

Therefore, it is expected that the risk of a repeated colonoscopy procedure is low.

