## **14. ASSESSMENTS OF MOTUS CLEANSING SYSTEM (MCS)**

The first 3 subjects of each physician will be excluded from the MCS performance evaluation in order to compensate for the system operation learning curve. Those subjects however will be included in the safety evaluation.

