#### **16.4. DEVICE TECHNICAL FAILURES**

Device deficiencies occurred within the colonoscopy procedure will be reported.

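### No planned analysis gives the post-procedure adequate rate with in-use technical failures and unreached segments counted as not adequate, and the sections on scoring incomplete procedures need reconciling

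*Combined protocol and SAP*

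**What the plan says.** All references are to the combined protocol and SAP.

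- **Technical failures.** Section 15.2.1 lists "System technical failure" among the reasons for excluding a subject from efficacy as missing or invalid data. It does not separate a fault found at the pre-examination check in section 12.5 from a failure after insertion.
- **Incomplete procedures.** Section 15.2.1 states that "the overall BBPS per patient will be evaluated based on the colon segments that were visualized". Section 15.2.2 likewise bases the primary assessment on the segments observed. Section 14.1 defines adequate as every colon segment graded 2 or above and applies this to incomplete procedures too. Section 14.1.2 describes the post-procedure score as covering the whole colon.
- **Missing data.** Section 15.5 says "No imputation of missing data will be performed".
- **Failed cecal attempt.** Under section 12.5 the procedure goes on with another colonoscope without the MCS, and the subject stays in the study.
- **Related outputs.** The plan provides individual failure listings (15.2.1), results by segment with counts, percentages and 95% confidence intervals (15.2.2), and the cecal intubation rate with its interval (15.2.4). Section 16.4 adds "Device deficiencies occurred within the colonoscopy procedure will be reported". Section 15.2 allows extra and post-hoc analyses.
- **Lead-in.** Section 14 says "The first 3 subjects of each physician will be excluded from the MCS performance evaluation".

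**The concern.** A failure after insertion is something the device did, not an absent measurement. Removing it takes out a case that a user of the device would count as unsuccessful. Scoring only visualized segments can also make a subject adequate although the right colon was never reached with the MCS.

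The post-procedure rate is the figure by which the documents describe the device: section 3.2 says earlier trials "demonstrated 95%-100% cleansing capabilities in poorly prepped subjects", section 4.4 says "MCS improved the cleansing level from 30% at baseline to 93% after the cleansing was operated", and section 15.1 uses 96%. Section 15.2.2 promises percentages with 95% confidence intervals, so the estimate is a planned result alongside the test. If cases of these two kinds occur, the reader gets a rate without them and no planned rate with them.

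**Working it through.** **1. The passages side by side**

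| Question | Sections 14.1, 14.1.2 | Sections 15.2.1, 15.2.2 |
|---|---|---|
| Which segments count? | All segments; whole colon | Those visualized or observed |
| Subject with an unreached segment, others 2 or above | Literally not adequate: one segment has no grade of 2 | Adequate |
| Failure after insertion | Not addressed | Removed as missing or invalid |

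Section 15.2.1 speaks of the overall BBPS, which could mean the summed score and not the adequacy call. Section 15.2.2 favours the seen-segments reading for the primary assessment. The text does not settle it.

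For segments seen after a switch to a colonoscope without the MCS, section 14.1.2 and the post-MCS wording of 15.2.2 point to MCS-only scoring. Section 15.2.2 also refers to everything observed during the colonoscopy, so this too needs stating.

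**2. The plan's own figure**

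Inputs from section 15.1: alpha 0.05 (two-sided assumed), power 0.80, switching proportions 0.6 and 0, so pd = d = 0.6.

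n = [z(0.975)·√pd + z(0.80)·√(pd − d²)]² / d² = [1.960·√0.6 + 0.842·√0.24]² / 0.36 = 10.35, rounded up to 11 pairs.

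This matches the protocol. Three sites give 33 evaluable subjects.

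**3. Post-procedure rate**

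Assumed base: 33 evaluable subjects at the 96% of section 15.1 is 31.7, taken as 32 adequate. Let a be in-use technical failures added back, and b incomplete cases that the seen-segments rule calls adequate.

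- Planned rate: 32/33.
- Comparator: (32 − b)/(33 + a), which cannot exceed 32/33 when a and b are zero or more.

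The documents give no values for a or b; those below are assumptions. Intervals are Clopper-Pearson.

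| a | b | Rate | 95% CI |
|---|---|---|---|
| 0 | 0 | 32/33 = 97.0% | 84.2 to 99.9 |
| 1 | 0 | 32/34 = 94.1% | 80.3 to 99.3 |
| 0 | 1 | 31/33 = 93.9% | 79.8 to 99.3 |
| 1 | 1 | 31/34 = 91.2% | 76.3 to 98.1 |
| 2 | 2 | 30/35 = 85.7% | 69.7 to 95.2 |
| 4 | 0 | 32/37 = 86.5% | 71.2 to 95.5 |

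The last row is an extreme: it fills the whole allowance in section 15.1 ("Addition of 10% of withdrawn subjects - 4 subjects") with in-use failures. If sections 14.1 and 14.1.2 govern, b is already zero and only a matters.

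**4. Significance test**

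Exact two-sided McNemar test, n = 33, alpha 0.05, affected share f independent of baseline.

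- Pre scores kept, affected subjects not adequate post: improving 0.6(1 − f), worsening 0.36f. At f = 10% these are 0.54 and 0.036, power 99.3%. At f = 20% they are 0.48 and 0.072, power 90.7%.
- Same completeness rule for pre and post: worsening is 0, and power exceeds 99.9% at both values.

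**The case against.** **Reach is a separate question.** The primary objective is cleansing, and cecal visualization has its own exploratory endpoint. A seen-segments score is a legitimate, prespecified measure of cleansing where the device got to. This stands, and is why the planned analysis should stay.

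**Much is already disclosed.** Failure listings, by-segment results, the cecal intubation rate and device-deficiency reports would let a reader rebuild part of the rate in so small a study. This stands in part: the reconstruction is partial and comes after the data are seen.

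**The plan does not forbid the analysis.** A reader might infer from section 15.5 that it does. That goes too far: section 15.2 allows additional analyses, and classing a failure as not adequate is an outcome definition, not imputation. What is missing is prespecification.

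**The direction follows from the comparator.** A reader might infer that the planned rate is inflated against any standard. It is not: if two excluded failures would both have been adequate, exclusion lowers the rate slightly, 32/33 = 96.97% against 34/35 = 97.14%. The direction for the pre-post difference is not fixed either.

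**The effect is hypothetical and small.** About 3 points per subject lies well inside the base interval of 84.2 to 99.9, the study is called a pilot, and no threshold is set for the post-procedure rate. All true. Yet the gap between the documents' own 93% and 96% is also 3 points.

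**Conclusion.** The point holds as a gap in reporting plus an inconsistency in wording. As written, in-use technical failures leave the efficacy set, the scoring of incomplete procedures is open to two readings, and no prespecified analysis counts either kind of case as not adequate.

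Compared with such an analysis, the planned post-procedure rate is equal or higher. The size depends on counts that the documents do not give: nil with no such case, and about 3 points per affected subject on the assumed base of 32/33.

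Two stronger readings are not supported. One is that the plan definitely scores a subject with an unreached segment as adequate; sections 14.1 and 14.1.2 can be read the other way. The other is that the primary conclusion is at risk; under the plan's inputs, exact power at 33 pairs stays at 90.7% or more with up to 20% affected. What is at stake is the rate and its interval.

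**What to change.** Keep the planned analysis and make these changes before the data are seen.

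1. **Reconcile** sections 14.1 and 14.1.2 with 15.2.1 and 15.2.2 on whether a subject with an unreached segment can be adequate.
2. **Add one supportive analysis** to 15.2.1 and 15.2.2, reported beside the post-procedure rate and its 95% confidence interval, in all non-lead-in subjects in whom the colonoscope with the MCS was inserted. Count as not adequate any subject without all three BBPS segments scored 2 or above with the MCS on withdrawal, whether because of a technical failure after insertion or an unreached segment.
3. **Keep observed scores** where a failure comes after all three segments have been scored with the MCS.
4. **Exclude and list**, with counts by cause, faults found before insertion and obstruction detected during colonoscopy, which section 11.3 makes an exclusion criterion.
5. **State** that segments seen only without the MCS do not enter the MCS post score.
6. **Apply the same completeness rule** to pre and post scores in any paired version.
7. **Clarify in 15.5** that this is an outcome definition and not imputation.

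The cost is wording in these sections and one extra table, with no added subjects or visits. The documents do not show whether the CRF records which segments were viewed with the MCS, so one field may be needed. The downside is a second, possibly less favourable rate that mixes reach with cleansing; the planned analysis still shows cleansing of the segments seen.
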